For each group session attended we will provide compensation (\$10) for travel expenses, as is consistent with attendance at clinical appointments for service-connected conditions through VA.

Starting with the second pilot group, a booster or follow-up session will be scheduled for 1 to 3 months following the end of the 9-session group. The purpose of this session is to check-in with

group members, discuss treatment gains and current symptoms, and to provide referrals and resources as appropriate. Veterans will also receive \$10 for attending this session.

Research Questions:

- Is the intervention feasible as conducted with older Veterans with PTSD?
- Are Veterans satisfied with the intervention?
- Do Veterans comply with assignments (e.g., monitoring forms)?

Data Analysis Plan: Baseline demographics (e.g., age, race, service era) will be summarized. To evaluate feasibility, we will descriptively examine recruitment and retention characteristics, such as ease of recruitment, number of sessions attended by participants, and study attrition. Secondly, we will examine compliance and satisfaction measures, such as participant and clinician ratings and participant feedback to gain a better understanding of the effectiveness of the groups in facilitating change and teaching group members about included concepts. Participant commitment will be evaluated by monitoring session attendance, compliance with assignments, and level of participation in group sessions. Participants' open-ended comments provided at the end of each session will be coded and categorized into themes, which will then be used to inform changes to the protocol as appropriate.

Phase III (Conduct Groups to Compare Intervention against Support Group):

Activity 1: The PI will provide training to group facilitators, compare the revised intervention protocol for older Veterans with PTSD against a support group control, and conduct three groups with the revised intervention protocol and three support groups, both among older Veterans with PTSD. Outcomes will be compared between intervention and support groups.

Activity 2: After the groups are completed, the group intervention protocol will be revised according to group member and facilitator feedback. The expert panel and mentors will be consulted prior to final revision of the protocol.

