Study staff may provide some technical assistance via telephone to participants at different points during their involvement in the study. Veterans who meet all telephone screening criteria other than “Has access to a home computer or device that will allow telehealth delivery of the intervention utilizing secure audio/video platforms (e.g. VVC, Webex) may receive assistance in connecting to secure platforms in order to determine if the home devices are sufficient to meet this criteria. Study staff may assist participants in connecting to complete the Informed Consent and baseline appointment process. Study staff may also assist participants prior to and following randomization to ensure that they are able to access the remote systems and utilize devices to participate in the group interventions. This assistance may include provision of telephone numbers and websites for VA technical support, methods to request VA-provided tablets, and trial sessions to work through potential issues (such as where to place cameras, how to maximize audio clarity, how to ensure privacy for the session, etc.).

Use of Email

Study staff may use e-mail to send remote access instructions or previously approved group handouts or measures to participants as needed (e.g. if postal mailing is delayed or participants ask for additional copies). Standard VA-approved language indicating that Veterans should not reply to these e-mails will be included in each e-mail.

Research Questions:

- Compared to support group participants, do intervention group participants experience greater increases in psychosocial functioning and quality of life and reductions in PTSD and depressive symptoms?
- Are pre-post changes maintained at 1 and 6 month follow-up?

Data Analysis Plan: Baseline demographics (e.g., age, race, service era) will be summarized for each condition (intervention and support groups). Descriptive statistics will be presented for all outcome variables. Prior to analyzing the data, the adequacy of randomization will be checked and any factors that are unbalanced between groups will be controlled for in group comparisons. Data will be analyzed using SPSS and Mplus. Change in primary outcomes (psychosocial functioning and quality of life) will be evaluated from pre- to post-intervention and at 1 and 6 month follow-ups. We will also evaluate change in secondary outcomes (e.g., PTSD and depressive symptoms).

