Hierarchical linear modeling (HLM)⁷² may be used to evaluate changes in these measures over time. HLM is an optimal strategy for analyzing change over time, with strengths such as handling missing data efficiently, providing powerful and accurate estimation procedures, and modeling flexibility. We will account for missing data by using full information maximum likelihood estimation. Intent-to-treat analyses will be conducted, and completers will be compared against drop-outs to determine any group differences. For our primary and secondary outcomes, we will specify a random intercepts and random slopes model in which Time, Condition, and the Condition x Time interactions will be included as predictors. Time will be coded by assessment time point (baseline, post-group, follow-ups) and modelled as a random effect to allow for individual differences in trajectories of change. We will examine between group effect sizes (e.g., Hedges g^{73}) for the intervention compared to the support group at post-group and follow-up assessments. Additionally, we will look at the portion of each group (intervention versus comparison) who experienced reliable change on primary outcomes. Given the developmental nature of this study, results may be used to provide preliminary data for a subsequent trial.

Assessments and Participant Compensation:

Focus group participants will be contacted by telephone after they have participated in order to collect individualized feedback and additional comments. Veterans who participate in the focus groups will be compensated \$75 for their time and participation.

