All Veterans who participate in Phase II and Phase III (intervention group pilot testing and comparison of group intervention with support group) will complete a structured diagnostic interview, baseline assessments, satisfaction ratings of each session, and post-group assessments. Phase III participants will complete one and six month follow-up assessments. Participants will be remunerated for their time and inconvenience. Baseline assessments (including the SCID questions) are estimated to take about 90 minutes and participants will be compensated \$20 for completion. Post-group and follow-up assessments are estimated to take 1 hour and participants will be compensated \$35 for each assessment they complete (Phase III participants will receive \$40 for completion of the six month follow-up). Additionally, all participants in Phases II and III will be remunerated \$10 to cover travel expenses for each group session they attend. Thus, Veterans who participate in Phase II could receive up to \$155 total and Veterans who participate in Phase III could receive up to \$230 total.

In case of a lapse between the time of baseline and the start date of the cohort, we may decide to reassess the participant and recomplete the baseline appointments. If the Veteran has a SCID lifetime rating, the SCID does not have to be recompleted; otherwise, both the SCID and the measures will be re-administered. In the event that this is the case, we will pay participants \$20 for their recompletion of the baseline.

Measures (see Table 2)

Note: This proposal is being written after publication of DSM-5 but prior to the release of appropriately updated assessment measures. Revised versions of all assessment measures that are available at the time the study is conducted will be used.

Phase IA: This is the protocol development phase. No participants will be enrolled or assessment measures collected during this phase.

Phase IB: Prior to being invited to participate in the focus groups for Veterans, potential participants will be screened over the telephone with the PC-PTSD-5.

All focus group participants will be contacted by telephone after attending the focus groups and asked several open-ended questions to gather feedback and allow participants a chance to share comments they may not have felt comfortable disclosing during the focus groups themselves.

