The Quality of Life Inventory (QOLI).⁷⁸ The QOLI is a 32 item self-report measure that assesses life satisfaction across 16 life domains (e.g., health, work, recreation). For each domain, the respondent rates how important the domain is on a 0-2 scale and how satisfied he or she is in this area of life on a 7-point scale. Satisfaction scores on the measure are weighted based on the respondent's rating of the importance of the life domain in order to achieve a total score. The measure was validated across a number of samples, including psychiatric inpatient and outpatient VA samples. Test-retest reliability was excellent over a one-month interval ($r = .91$) as was the internal consistency of the measure (alphas ranged from .86-.89). The measure also demonstrated convergent and discriminant validity with other measures of life satisfaction.

The Inventory of Psychosocial Functioning (IPF).⁷⁹ The IPF is an 80-item self-report measure designed to assess multiple domains of functional impairment experienced by Veterans. Respondents rate how often they have acted a certain way over the past 30 days. Items are rated on a 7-point scale ranging from 0 ("never") to 6 ("always"). The IPF yields a total score and scores for seven subscales: romantic relationships, family, work, friendships and socializing, parenting, education, and self-care functioning. Respondents have the option to skip sections that do not apply to them. The IPF has excellent internal consistency reliability (overall alpha = .93) and the scale correlates with other self-report measures of quality of life and functional impairment, such as the QOLI ($r = .59$).

Measures to be Completed by Veterans at Each Group Session:

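### Phase III lets observed imbalance choose the covariates and specifies neither own-baseline adjustment nor a therapy-group term for effect sizes that will be used to plan a larger trial

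*Combined protocol and SAP*

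**What the plan says.** The relevant text is in the Data Analysis Plan under Phase III.

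- Covariates: before analysis, "the adequacy of randomization will be checked and any factors that are unbalanced between groups will be controlled for in group comparisons". No covariate is named and no threshold for imbalance is given.
- Outcomes: "Change in primary outcomes (psychosocial functioning and quality of life) will be evaluated from pre- to post-intervention and at 1 and 6 month follow-ups".
- Model: hierarchical linear modelling "may be used to evaluate changes in these measures over time". If it is used, "Time, Condition, and the Condition x Time interactions will be included as predictors", with random intercepts and slopes for individuals, full information maximum likelihood and intent-to-treat analysis. Baseline is one of the time points. The plan does not say whether time is categorical or numeric.
- Effect sizes: between-group effect sizes, with Hedges g as the example, "for the intervention compared to the support group at post-group and follow-up assessments". The numerator and the SD are not stated.
- Delivery: Activity 1 of Phase III is to "conduct three groups with the revised intervention protocol and three support groups". The model has no term for these six groups.
- Use: Activity 3 of Phase III and the section on limitations for future research both send the effect sizes to the planning of a larger randomised trial.

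**The concern.** Under proper randomisation any baseline imbalance is due to chance, so checking for it and then adjusting lets the data pick the model. With a target of about 60 Veterans, some imbalance is likely, and two analysts could reasonably arrive at different covariate sets.

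The covariate most likely to help, the outcome's own baseline score, is not prespecified. Because the model includes a Condition term, the arms are free to differ at baseline. With categorical time its contrasts are therefore a difference at the visit or a difference in change, and neither uses the baseline as efficiently as adjustment does.

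Veterans treated in the same therapy group may also have correlated outcomes. If so, an analysis with person-level random effects only will report intervals that are too narrow. Because the next trial is to be sized from these estimates, both the way g is built and the honesty of its interval matter.

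**Working it through.** **Inputs from the documents.** Three groups per arm with a target of 10 members each (Phase III, Recruitment and Participant Characteristics), and up to 14 per group (Human Studies Section). The only sample-size figure reproduces as a head count: 6 × 14 = 84 recruited. At target size, 6 × 10 = 60, so n = 30 per arm with equal arms assumed. No alpha, power or target effect is given.

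**Assumed inputs.** The correlation r between baseline and post-group score is not given. The nearest figure is for the QOLI: "Test-retest reliability was excellent over a one-month interval", with r = .91. That is not a correlation across treatment, so I use r = 0.3 to 0.91. The therapy-group intraclass correlation (ICC) is not given; I use 0, 0.05 and 0.10.

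**Variance of the arm difference.** Assume equal SDs of 1, complete data, categorical time and a baseline that is not clustered. Let D = 1 + (m − 1) × ICC, with m the group size. In units of 2/n:

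- post-visit contrast: D
- change contrast: D + 1 − 2r
- baseline-adjusted contrast: D − r²

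With no clustering (D = 1):

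| r | post | change | adjusted | cut vs post | cut vs change | cut vs better |
|---|---|---|---|---|---|---|
| 0.3 | 1 | 1.40 | 0.91 | 9% | 35% | 9% |
| 0.5 | 1 | 1.00 | 0.75 | 25% | 25% | 25% |
| 0.7 | 1 | 0.60 | 0.51 | 49% | 15% | 15% |
| 0.8 | 1 | 0.40 | 0.36 | 64% | 10% | 10% |
| 0.91 | 1 | 0.18 | 0.172 | 83% | 4.5% | 4.5% |

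Post and change cross at r = 0.5, so the cut over the better one peaks there. Estimating the slope multiplies the adjusted variance by 1 + 1/(2n − 4) = 1 + 1/56 = 1.018, so 25% becomes 1 − 0.75 × 1.018 = 24%.

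**With clustering.** The maximum cut over the better contrast is 0.25/D, again at r = 0.5:

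- m = 10: 0.25/1.45 = 17.2% (ICC 0.05); 0.25/1.90 = 13.2% (ICC 0.10)
- m = 14: 0.25/1.65 = 15.2%; 0.25/2.30 = 10.9%
- m = 10 with ICC 0.01 or 0.20: 0.25/1.09 = 23%; 0.25/2.80 = 9%

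**Coverage if clustering is ignored.** At r = 0.7 and m = 10, the ratio of reported to true variance is about 1/1.45 (post), 0.60/1.05 (change) and 0.51/0.96 (adjusted) at ICC 0.05. At ICC 0.10 it is 1/1.90, 0.60/1.50 and 0.51/1.41. Multiplying 1.96 by the square root of each ratio gives coverage of about 90%, 86% and 85%, then 84%, 79% and 76%. Simulation (20,000 trials per setting) gave 90%, 86% and 85%, then 84%, 77% and 75%. Adjustment without a group term covers worst, because it shrinks the individual-level variance and leaves the group-level variance untouched.

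**Intervals built on therapy groups.** Six groups less two arms leaves 4 degrees of freedom (t = 2.776). Simulated coverage was about 95%. Mean half-widths at r = 0.7 were 0.81, 0.69 and 0.66 SD (post, change, adjusted) at ICC 0.05, and 0.92, 0.82 and 0.80 SD at ICC 0.10.

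**If time is linear instead.** Take four equally spaced visits, r = 0.5 from a random intercept, no clustering, and a truly linear course. In units of 1/n, the planned model's fitted post-group difference has variance 2 × [0.5 + 0.5 × (1/4 + 0.25/5)] = 1.30, against 2 × 0.75 = 1.50 for single-visit adjustment. Its Condition × Time contrast to post-group has 2 × 0.5/5 = 0.20. A common baseline mean within the same linear model gives 2 × (0.10 − 0.15²/0.85) = 0.147.

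**The case against.** The best defence is that baseline is already in the analysis: change is evaluated, baseline is a time point, and likelihood estimation with intent-to-treat is planned. A reader might infer that the plan ignores baseline or yields a biased comparison. The documents do not support that: the planned model is valid under randomisation, and what is lost is precision.

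A second objection is that random slopes suggest numeric time, and under linear time single-visit adjustment can lose to the fitted difference (1.50 against 1.30 above). This stands. The precision claim is therefore conditional on categorical time, and the common-baseline-mean form is the safer route because it improves the Condition × Time contrast in the linear model too.

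Third, the gain is modest: 25% of variance is about 13% of the standard error, and 13–17% is about 7–9%, in a study the plan calls small and developmental. That also stands, but the effect sizes are a stated product of Phase III, and the coverage problem is the larger of the two.

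Fourth, the coverage of the group-based interval was checked only with groups of exactly 10 and one complete visit, whereas drop-out is expected. An ICC estimated from six groups will also be very imprecise.

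Two further inferences go too far. One is that g is undefined: the plan names the statistic, the comparison and the visits, and leaves open only the numerator and SD. The other is that there is no single baseline, because after a lapse before the cohort starts "we may decide to reassess the participant and recomplete the baseline appointments". That reads naturally as replacement. Under the telehealth procedure, Veterans join the randomisation list only after baseline forms and the interview are complete. Both are details to write down, not errors.

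**Conclusion.** The point holds as a recommended improvement. The plan lets observed imbalance select covariates, does not prespecify adjustment for each outcome's own baseline, and states no therapy-group term.

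With categorical time and complete data, adjustment is never less precise than the post-visit or change contrast, apart from the small cost of estimating the slope. The 25% ceiling applies only against the better of the two; against one alone the cut can be much larger, for example 49% below post-only at r = 0.7. The 13–17% figure is not a bound: it rests on an assumed ICC of 0.05–0.10 and groups of 10, and becomes 11–15% with groups of 14.

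The therapy-group term adds no precision; it corrects the stated uncertainty. At r = 0.7 and the assumed ICCs, intervals that ignore clustering cover about 84–90% (post-only) or 75–85% (adjusted). Whether clustering exists here is unknown, since the documents give no ICC. Because adjustment alone makes undercoverage worse, the two changes should be made together.

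**What to change.** In the Phase III Data Analysis Plan:

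1. Drop the imbalance trigger. Keep the baseline table as description and name any further covariates in advance.
2. Prespecify adjustment of every outcome for its own baseline, preferably through a common baseline mean for both arms in the mixed model. State how time is coded, and make the model definite rather than optional.
3. Add a therapy-group term, or a group-based interval, with small-sample degrees of freedom (about 4).
4. Define the numerator of g as the model-adjusted difference at each visit in all randomised Veterans, name the SD (the pooled unadjusted baseline SD is one reasonable choice) and the small-sample correction, and report g with the interval from item 3.
5. State which score counts if the baseline was repeated, and whether it was taken before allocation was known.
6. Report the baseline-to-post correlation, the SD at each visit and the ICC with a caution on its imprecision. Plan the next trial from the interval, not the point estimate alone.

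No new data are needed, since Table 2 already collects the outcome measures at baseline. The cost is one degree of freedom per model and wider intervals. At r = 0.5 with groups of 10, the adjusted group-based interval is about 1.5 times (ICC 0.05) to 1.8 times (ICC 0.10) the width of a post-visit interval that ignores clustering: 2.776 × √1.20 / 2.00 = 1.52 and 2.776 × √1.65 / 2.00 = 1.78.

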level psychologist who is not part of the study team and is familiar with cognitive-behavioral interventions for PTSD. Each group session will be digitally recorded, and the monitor will listen to a randomly selected sample (20% of the sessions) and complete a fidelity monitoring form. Group facilitators will also provide ratings and feedback at the end of each session. Following the last session, Veteran participants will be asked to complete post-group assessment measures. Veterans will be asked to complete follow-up assessments at one month and six months, either via postal mail or in person.

Consistent with the recruitment method followed in Phase II, Veteran participants for both the intervention and support groups will be recruited from the PTSD and Geriatric Mental Health Clinics if they are new patients, if they are established patients but have declined or dropped out of more structured trauma-focused EBPs, if they have partial PTSD, or if they are deemed inappropriate for trauma-focused therapy due to health impairments or other reasons. The same procedure will be followed as in Phase II after the six month follow-up. Specifically, Veterans will be presented with descriptions of a variety of evidence-based treatments, including trauma-focused EBPs, and provided with referrals should they request them. Attitudes toward treatment and readiness for change will also be assessed. In addition, the VA electronic medical records will be reviewed to document enrollment and completion of mental health treatment at the six month follow-up.

Groups will be conducted during regular business hours. [name] (the PI) is a licensed clinical psychologist, and will be available during screening calls, baseline and follow-up assessments, and during group sessions in case of a clinical emergency. If needed, the PI will be contacted to conduct a risk assessment with a patient, and if it is determined that immediate care is needed, will walk the participant down to urgent care. The PI will also have referral information and important resources (e.g., the Veteran's crisis line, suicide prevention coordinator numbers) available. In the event that the PI is not available to provide clinical coverage, another licensed provider will be asked to provide coverage.

For each group session attended we will provide compensation (\$10) for travel, a practice that is consistent with VA policy to reimburse for travel expenses for VA appointments for service-connected conditions.

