Groups will be conducted using a telehealth platform that has options for video and telephone-only participation (such as WebEx). Participants will be sent email invitations that contain links to join the sessions. Video sessions will start 10 minutes prior to the session start time, to provide participants enough time to work through any technological issues with study staff prior to the start of the sessions. Study participants will be asked to provide verbal consent to participating in the virtual telehealth sessions at the start of the first session, after being informed about the limits of confidentiality and important safety issues. The participants will be reminded of these issues at the beginning of the remaining sessions, but will not be verbally re-consented each week. Additionally, participants will be reminded that the session is being audio-recorded. The study PI, a licensed psychologist, or another licensed clinician will be available by phone following the sessions in case any of the participants indicate experiencing distress. Veterans will receive \$10 per session that they attend. Payments will be mailed via check through the agent cashier at two timepoints: after session 4, and after session 9.

Prior to the start of group sessions, participants will be sent a package of all assessments to be completed in sessions, along with a pre-addressed, stamped envelope. Assessment measures will be clearly labeled with Veteran ID, session #, and whether the measure is to be completed at the start or at the end of the group session. During each session, group leaders will facilitate the completion of measures at the start and the end of each group session, and participants will be asked to indicate when they have finished measures and placed them in the included envelope to be returned at the end of the 9 weeks. Study staff will send replacement assessment measures as needed, through postal mail or e-mail.

Post-Assessment and Follow-Ups

Following the last session, Veteran participants will be asked to complete post-group assessment measures (which will be mailed to them). The follow-up booster session will also be conducted over a telehealth platform. Veterans will be asked to complete follow-up assessments at approximately

one month and six months via postal mail. Appropriate clinical referrals will be provided following the end of study participation.

Technical Assistance

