Focus group participants will provide data in the form of audio recordings that will be transcribed, demographic information, and responses to survey measures. Veterans participating in the pilot intervention groups and the comparison condition (intervention and support groups) will provide data in the form of self-report assessment measures collected during and after group participation. Veteran participants will be recruited using data from a roster of Veterans who have sought treatment through the VA National Center for PTSD or PTSD clinic. This roster is an electronic database maintained by the VA National Center for PTSD – Behavioral Science Division. Participant entry into the database is done on a voluntary basis and written consent for future contact has already been established.

(c) Potential risks. The potential psychological, physical, social or other risks to Veterans who participate in the proposed study are minimal. Veteran focus group participants will be discussing domains of psychosocial functioning that they view to be problematic for themselves or for other Veterans. Additionally, Veterans who participate in the intervention groups will be asked to complete psychological and psychosocial assessment measures and discuss areas of difficulty for them. There is a slight chance that Veterans discussing these issues may experience some psychological discomfort when reflecting on such experiences. [name] (the PI), as a trained clinical psychologist, will be able to provide thorough assessment in the event of a participant's adverse reaction to focus group participation. In addition to [name], another licensed clinical psychologist will be available during each of the focus groups. If a Veteran becomes distressed and it is clinically appropriate, the Veteran will be allowed to leave the group and speak with the available psychologist. If clinically appropriate, the Veteran will participate for the remainder of the focus group and [name] will speak with him individually as the group is over to assess distress and any other clinical

needs. Appropriate intervention and/or referral for treatment can be provided, if needed. No other known physical, social or legal risk associated with participation in the proposed research project is identified.

(2) Adequacy of Protection from Risks

(a) Recruitment and informed consent.

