(b) Protection against risk. The primary risk associated with the proposed study includes psychological distress resulting from increased focus on psychosocial problems during the assessment, focus group, and/or intervention sessions. To address this potential risk, [name], a trained clinical psychologist, is in a good position to provide further evaluation of a participant's distress. This evaluation may include contact with a participant's current healthcare providers, including mental health professionals, if needed. [name] will also be in a good position to make referrals for further evaluation and/or treatment, and to ensure that such consults are placed on the participant's behalf. Study staff will immediately report any serious adverse events to [name], and she will, according to standardized procedures, report them to the IRB within the required timeframe. In addition, all participants will be provided with [name] contact information, and encouraged to establish contact at any time during the study as needed. All other incidents (e.g., theft or loss of data), will be reported in accordance with VA policy. Efforts will be made to protect confidentiality. Focus group members will be asked not to discuss information about other individuals in the group outside of the group setting. Participants will be asked not to state their names when speaking in order to protect confidentiality on the audio recordings of the focus group sessions. Study staff will immediately report any serious adverse events to the PI. The PI will, according to standardized procedures, report them to the IRB within the required timeframe. The confidentiality of the data that is gathered from participants (audio recorded group sessions, telephone screen data, survey measures) will be protected through secure storage of such media in a locked cabinet in [name] office that is kept locked when unattended. Data will be de-identified by removing all individually identifiable (all 18 HIPAA identifiers) prior to data analysis. The PI will provide members of the research team with de-identified datasets as needed. Once research staff are no longer working on the study, they will be removed from the protocol. All information kept electronically, including digital recordings of focus groups, will be kept behind the VA firewall on a secure server in a restricted access computer file. Records will be destroyed in accordance with the VA Record retention schedule (www1.va.gov/VHAPUBLICATIONS/RCS10/rccs10-1.pdf). Records will be destroyed,

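### The plan measures distress on a schedule in both arms but plans no by-arm count of Veterans who reliably worsened and no scheduled adverse-event enquiry

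*Combined protocol and SAP*

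**What the plan says.** **Risk.** Under Protection against risk, the Human Studies Section states: "The primary risk associated with the proposed study includes psychological distress resulting from increased focus on psychosocial problems". Under Potential risks it adds: "No other known physical, social or legal risk associated with participation in the proposed research project is identified".

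**Adverse events.** The reporting rule is "Study staff will immediately report any serious adverse events to the PI", and the PI then informs the IRB. Participants receive contact details and are "encouraged to establish contact at any time during the study as needed". In the telehealth format a clinician is reachable after sessions "in case any of the participants indicate experiencing distress". The text contains no scheduled adverse-event question, no log of non-serious events and no by-arm table of events.

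**Scheduled measurement.** At each session Veterans rate their current distress and whether they are better or worse than at the previous session, and report nightmares, flashbacks and anger outbursts (Measures to be Completed by Veterans at Each Group Session; carried into Phase III). Table 2 lists the DASS-21, PCL and BDI-II as additional outcomes measured repeatedly. The Phase III measures paragraph extends the baseline and post-group scales to one and six months.

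**Analysis.** Descriptive statistics are promised for all outcome variables. A random-intercept, random-slope model with Condition, Time and their interaction covers primary and secondary outcomes. At the level of the individual, "we will look at the portion of each group (intervention versus comparison) who experienced reliable change on primary outcomes". Table 2 places the QOLI, IPF and VR-12 under that label.

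**Record review.** In the Phase III Procedure, "the VA electronic medical records will be reviewed to document enrollment and completion of mental health treatment at the six month follow-up".

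**The concern.** The one individual-level analysis is confined to the primary outcomes and is unsigned, while the named risk is measured mainly by scales outside it. The symptom scales are compared through means and slopes, and improvement in most participants can hide worsening in a few. Both arms are active groups, so a Condition x Time effect says nothing about worsening common to both.

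Serious psychiatric events have no systematic source. Staff use the electronic record at screening to find recent hospitalization for suicidal ideation or psychosis, which is an exclusion. The six-month review of the VA record is not asked to look for the same event.

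The study is meant to supply pilot data for a larger randomized trial. As written, its report need not state how many Veterans in each arm got worse, and a statement that no serious events were reported could not be told apart from one that none were looked for.

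**Working it through.** The documents give no harm rate, alpha or power for Phase III, so there is no harm figure to reproduce. The recruitment figure does reproduce: 6 groups x 14 = 84.

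**Inputs from the documents.** Three groups per arm with a target of 10 each gives 3 x 10 = 30 per arm; at up to 14 each, 3 x 14 = 42. QOLI test-retest reliability is 0.91. No reliability is given for the BDI-II, PCL or DASS-21. All rates, shifts and the ICC below are assumptions.

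**1. Mean against count.** If 80% improve by 0.5 SD and 20% worsen by 1 SD, the mean change is 0.80 x 0.5 - 0.20 x 1.0 = 0.2 SD of improvement, although one in five is worse. If 10% worsen by 1 SD and the rest do not change, the arm mean moves by 0.10 x 1 = 0.1 SD.

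**2. The threshold matters.** With reliable change set at 1.96 x sqrt(2(1 - r)) SD:

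| r | Threshold (SD) |
|---|---|
| 0.91 (QOLI) | 0.83 |
| 0.80 (assumed) | 1.24 |

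A worsening of 1 SD is counted only if r is at least 1 - (1/1.96)²/2 = 0.87. Whether the Veterans in step 1 are counted therefore depends on each scale's reliability, and the threshold must be fixed beforehand.

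**3. What a count could show with complete data.**

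| Quantity | n = 30 per arm | n = 42 per arm |
|---|---|---|
| Upper bound after 0 cases, 1 - 0.05^(1/n), one-sided 95% | 9.5% | 6.9% |
| Chance of at least one case at a true 5%, 1 - 0.95^n | 0.79 | 0.88 |
| 95% half-width for the arm difference at 10% each, 1.96 x sqrt(2 x 0.1 x 0.9/n) | 15 points | 13 points |
| Power, 5% v 15%, two-sided 0.05, normal approximation | 0.25 | 0.33 |
| Same, Fisher's exact test | 0.09 | 0.20 |
| Same, normal approximation with ICC 0.10 | 0.15 | 0.17 |

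The last row divides n by 1 + (m - 1) x ICC, which is 1.9 for m = 10 and 2.3 for m = 14. The other rows ignore clustering within therapy groups. The first row is a best case: it holds only if every randomized Veteran is ascertained, and it does not measure what would be missed.

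**4. Do the other sources close the gap?** The session ratings come from attendees and end with the sessions. In telehealth the forms are posted back after nine weeks, and no analysis of these ratings is named. Drop-outs are contacted about their reasons for leaving, but the stated use is to inform later phases and later work. The DASS-21 is not named in the analysis plan, whose examples of secondary outcomes are PTSD and depressive symptoms. Random slopes allow for individual differences in trajectory but yield no count of who worsened.

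**The case against.** The strongest reply is that harm is already well covered. Distress and better/worse ratings are taken at every session and three symptom scales are repeated. Secondary outcomes are described and modelled by arm, drop-outs are contacted, and in-person follow-up is allowed outside the telehealth format. The VR-12, a primary outcome, has a mental component score, and unsigned reliable change does not exclude worsening. The study rates its risks as minimal and its comparisons as preliminary, and serious-event reporting follows standardized procedures that are not reproduced here.

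Much of this stands, and it rules out stronger readings:

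- A reader might infer that harms are recorded only if staff happen to hear of them. That describes serious adverse events, not symptom scores.
- A reader might infer that the trial cannot say whether either arm made Veterans worse. The data will be in hand and average symptom change by arm is planned; what is missing is a planned count.
- A reader might take the long stretch after session 9, with few live contacts, as a measure of missed events. Calendar time is not a count of events, and the number of contacts depends on the format.
- A reader might suppose that drop-outs are the people most likely to have been harmed. Nothing in the documents shows this.

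The reply does not supply a signed individual-level analysis of the symptom scales, a scheduled enquiry about events, or a by-arm table of either. Low power is a reason to label the table descriptive, not to leave it out.

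**Conclusion.** The concern holds as a gap in the analysis plan and the adverse-event procedure, not in the measurement of distress. Nothing commits the report to stating, by arm, how many Veterans reliably worsened on distress or symptoms or had a serious psychiatric event.

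The gap is moderate and the change is worth making because it is cheap. At 30 to 42 per arm the result would be counts with wide intervals: about 13 to 15 points either side of an arm difference if 10% worsen in each arm. It would not be a test, and without an untreated arm it could not attribute worsening to the groups. The example of a hidden worsening minority rests on assumed proportions and shifts. It shows that a mean can conceal worsening, not that it will here.

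**What to change.** 1. **Phase III Data Analysis Plan.** For the BDI-II, PCL and DASS-21 as well as the primary outcomes, report by arm the number with reliable improvement, no reliable change and reliable worsening. Do so at post-group, one month and six months, out of all randomized, with missing as its own category and exact intervals. State the threshold in advance from each scale's reliability, for example 1.96 x sqrt(2(1 - r)) SD, and give the source of r.
2. **Phase III Procedure.** Have the six-month record review also abstract psychiatric hospitalizations, emergency mental-health visits and deaths since randomization for every randomized Veteran, including drop-outs. Add a yes/no hospitalization item to the one- and six-month forms, because Veterans who do not use the VA may enroll.
3. **Reporting.** Tabulate events by arm, label the comparison descriptive, and state that drop-outs outside the VA who return no form remain unascertained.

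The cost is one table from data already collected, a few fields in a review already planned, one item on two forms, and the amendment to add them. More events will be counted than under passive reporting, and the report should say so. No treatment or clinical rule changes.
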